In this context of promoting healthy eating and based on the characterization of the western diet, which does not meet the daily requirements for essential fatty acids (EFAs) and fat soluble vitamins such as vitamin E, the present research project aims to describe the effect of daily consumption of two fermented dairy beverages supplemented with dietary sources high in tocotrienols and ALA on classical biological markers of cardiovascular disease (CVD) and vitamin E, over a period of three months, in individuals with cardiovascular risk. The products are currently being developed as part of a doctoral thesis in the Food Science and Technology program at the Universidad Nacional de Colombia, Bogotá campus, Faculty of Agricultural Sciences. If satisfactory results are obtained, new dairy products could be developed for the Colombian market, promoting the cultivation of Sacha INchi and Palm by diversifying the use of their fruits as sources of bioactive compounds. The present research proposal aims to answer the following question: what is the effect of consuming yogurts fortified with dietary sources of omega-3 and vitamin E on cardiovascular disease biomarkers and vitamin E in healthy adults?

OBJECTIVES

General: Evaluate the effect of consumption of two fermented dairy beverages fortified with SIO and HPO, on the lipid profile and vitamin E, in individuals at risk of CVD.

Specifics:

1. Describe the health, nutritional status and intake of the individuals before and after the intervention.
2. Establish the changes over time in the lipid profile, Apo A, Apo B and vitamin E in the blood after the intervention.

MATERIALS AND METHODS

The study will be presented to the research and ethics committee of the Faculty of Sciences of the Pontificia Universidad Javeriana. The effect of consumption of fermented dairy beverages fortified with SIO and HPO will be evaluated on the response variables: plasma lipid profile (HDL-C, LDL-C, Triglycerides, TC), Apolipoprotein A, Apolipoprotein B and vitamin E level in blood.

Type of study

An experimental study will be carried out consisting of a controlled clinical trial with three arms, each of which will be determined by the administration of two oils and a control. The oils will be transported into a fermented milk drink. Participants will be selected using a criterion of convenience through a call at the

 
Pontificia Universidad JAVERIANA Colombia
	
Research registration PUJ
	
Version: 1

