
Investigation project
		

Pontificia Universidad Javeriana. As a result, it is expected to select 66 individuals, 50% men and 50% women, who meet the inclusion criteria. Individuals will be stratified by sex and will be randomized in equal numbers to each of the three treatment groups, such that each treatment group will have 33 people in which the sexes will be equally distributed.

The sample size was determined taking into account the literature in which the same biomarkers have been evaluated (Brenna, Plourde, Stark, Jones, & Lin, 2018; Gonzales & Gonzales, 2014; Nayebifar, Ghasemi, & Karimipour, 2020; Qureshi, Sami, Salser, & Khan, 2001, 2002). It is important to highlight that to date there are no studies that contemplate the two oils carried in a fermented drink; even though there are studies with hybrid palm oil, alone and in other foods, there are none with Sacha Inchi oil, for the postulated response variables. Upon encountering this panorama, this study will provide a parameter to determine the sample size in subsequent studies. Finally, the postulate of the Food and Drug Administration (FDA) was taken into account, which states that the total number of subjects and patients included in Phase 1 studies varies with the drug, but is generally in the range of 20 to 80 subjects (FDA, 2019), so it is considered that it can also be applied as a criterion for foods since the guidelines for drug testing are rigorous.

Following these criteria, it was determined to take 54 subjects in total with an oversample of 20% (66 individuals in total) to compensate for possible dropouts during the follow-up stage. Compliance with the proposed number of participants and the collection of their blood samples will be subject to the evolution of the Covid-19 pandemic and government preventive isolation guidelines.

Target population

Inclusion criteria: adult men <50 years old and women <40 years old, healthy, with TC levels $\geq 200\text{mg/dl}$, with regular consumption of fermented milk beverages at least three times/week, with a maximum level of moderate physical activity and who sign the informed consent.

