1. Control: corresponds to the subjects who will be given a fermented milk drink
2. Treatment 1 corresponds to the subjects who will be supplied with the fermented milk drink with total replacement of milk fat matter with SIO.
3. Treatment 2 corresponds to the subjects who will be supplied with the fermented milk drink with total replacement of milk fat matter with HPO.

 
Pontificia Universidad JAVERIANA Colombia
	Research registration PUJ	Version: 1
	Investigation project	

Phase III

In this phase, the results will be shared with the study participants and a final assessment.

Statistical analysis

A socio-economic-demographic characterization of the population will be carried out, by means and standard deviation and ranges. A database will be created in Excel and the intake will be analyzed using the Menus Plus 2018 software. To analyze data from blood samples, a repeated measures analysis of variance will be applied. Kolmogorov and Cramér-von Mises tests will be used to evaluate the Gaussian nature of the variables. Tukey-adjusted p values will be applied to examine differences between treatments. STATGRAPHICS CenturionXVIII software will be used.

POSSIBLE RESEARCH RESULTS

With this research, the characterization of the nutritional status, health status and quality of the diet of the target population will be obtained. Furthermore, after the intervention with fortified yogurts, it is expected to observe an improvement in the blood lipid profile parameters, Apo A, Apo B and vitamin E, of the participants compared to the initial values, which would minimize the risk of associated CVD associated to lipoproteins.

Expected products

Category	Product	Amount	Description
Other outreach products	Documentary Production	1	Submission of at least 1 scientific article in an indexed journal.
Presentation at scientific event	Presentation of paper or poster at international event	1	Participation in a conference related to the topic of clinical nutrition or food science and technology.
Project formulation and submission	Formulation and submission of other projects	1	Another project related to the characterization of the mechanism of the bioactive compound.

PARTICIPATING INSTITUTIONS

Participating entity/institution name	Temporal	Main financier	Other financier	Executor	Co-Executor	Assesment entity
UNIVERSIDAD NACIONAL DE COLOMBIA - BOGOTÁ	No	No	Yes	No	Yes	No
PONTIFICIA UNIVERSIDAD JAVERIANA (PUJ)	No	Yes	No	Yes	No	No

TEAM OF PONTIFICIA UNIVERSIDAD JAVERIANA

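### Entry requires TC of at least 200 mg/dl and benefit is described as change from initial values, but the plan does not say that the contrast with the control yogurt decides efficacy

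*Combined protocol and SAP*

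**What the plan says.** All references are to the Combined protocol and SAP.

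- **Target population, inclusion criteria:** TC must be at least 200 mg/dl, a one-sided cut. No repeat or averaged qualifying measurement is described.
- **Objectives, specific objective 2:** "Establish the changes over time in the lipid profile, Apo A, Apo B and vitamin E in the blood after the intervention". No comparator is named.
- **Possible Research Results:** the markers are expected to improve "of the participants compared to the initial values", and a lower lipoprotein-related cardiovascular risk is inferred from that. The control yogurt is not mentioned.
- **Type of study:** the design is "a controlled clinical trial with three arms", and participants "will be randomized in equal numbers to each of the three treatment groups".
- **Statistical analysis:** for the blood markers, "a repeated measures analysis of variance will be applied", and "Tukey-adjusted p values will be applied to examine differences between treatments". The section does not give the model's factors, the handling of baseline, or the term on which efficacy is decided.

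**The concern.** A marker that had to be high for entry tends to be lower when measured again, with no treatment at all. If the qualifying sample also serves as baseline, TC should fall in all three arms, control included. The time effect of the repeated-measures ANOVA absorbs that fall and does not estimate the effect of either oil.

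The plan names an analysis that could separate the two, but does not say that it decides. Objective 2 and the expected result both point to the time effect. *Differences between treatments* is also ambiguous in this model: it can mean the treatment main effect, the arm-by-time term, or a comparison at follow-up. At stake is whether a fall from baseline in an oil arm could be reported as a benefit when the control arm fell as much.

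**Working it through.** The plan gives no effect size, SD, alpha or power, so it has no figure of its own to reproduce here. The one design number used is 18 evaluable participants per arm (Target population; 54 / 3 = 18).

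**Assumptions, not in the documents:** source-population TC mean m = 180 to 200 mg/dl, SD s = 35 to 40, reliability of a single measurement r = 0.7 to 0.9, normal distribution, no product effect, and the qualifying sample used as baseline.

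**Formulas**
- z = (200 - m) / s, and L = phi(z) / (1 - Phi(z)).
- Expected fall = (1 - r) × s × L.
- Variance of TC at entry = s² × (1 + zL - L²).
- Variance of change = (1 - r)² × variance at entry + s² × (1 - r²).
- Probability of a significant within-arm fall: two-sided 5% paired t-test, noncentral t with 17 df, noncentrality = fall / (SD of change / √18).
- At least one of the two oil arms: 1 - (1 - p)².

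**Mid case (m = 190, s = 40, r = 0.8)**
- z = 0.25 and L = 0.9636, so the fall = 0.2 × 40 × 0.9636 = 7.7 mg/dl.
- Variance at entry = 1600 × 0.3124 = 499.9.
- SD of change = √(0.04 × 499.9 + 1600 × 0.36) = 24.4.
- Noncentrality = 7.71 / (24.41 / 4.243) = 1.34, so p = 0.24.
- At least one oil arm: 1 - 0.757² = 0.43.

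**Range**

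| m | s | r | Fall (mg/dl) | SD of change | One inert arm | At least one of two oil arms |
|---|---|---|---|---|---|---|
| 200 | 35 | 0.9 | 2.8 | 15.4 | 0.11 | 0.21 |
| 190 | 40 | 0.8 | 7.7 | 24.4 | 0.24 | 0.43 |
| 180 | 35 | 0.7 | 12.5 | 25.6 | 0.50 | 0.75 |
| 180 | 40 | 0.7 | 13.7 | 29.2 | 0.47 | 0.71 |

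Without regression to the mean, a significant fall in one arm would have probability 0.025, half of the two-sided 5%.

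**Simulation under the same assumptions** (three inert arms of 18, 4000 runs per scenario)
- The pooled time effect shows a significant fall in 26% to 94% of trials (mid case 63%).
- The Tukey comparison of change between arms has a family-wise error of 4.3% to 5.8%, about the nominal 5%. The expected difference between arms is zero.
- If the baseline is a separate sample taken after qualification, the expected spurious change in the mid case is about 0, against a fall of 7.7 mg/dl when one sample serves both purposes.

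**Treatment main effect.** With one sample before and one after, arms equal at baseline and a true follow-up difference d, the main effect averages the two times: (0 + d) / 2 = d / 2. Read this way, the between-arm comparison stays valid but halves the difference of interest.

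**The case against.** The strongest reply is that the trial is randomised and controlled, and that Tukey-adjusted differences between treatments are already planned. That set contains each oil yogurt against control, and regression to the mean has the same expectation in every randomised arm. This stands. A reader might infer that the plan will judge benefit on before-after change and ignore its control arm. The documents do not support that: the sentence about initial values is a forecast under Possible Research Results, not a decision rule, and objective 2 does not exclude comparing changes between arms.

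Three further limits also stand:
- No within-arm paired test is planned. The 0.11 to 0.50 describes what follows if the expected-result wording is acted on, not the planned test. The time effect, however, is a standard output of the planned ANOVA.
- The readable text does not say that the qualifying sample is the baseline. The study-design figure, which might show sampling times, is not available here.
- Selection is on TC alone. LDL-C and Apo B would fall only as far as their chance variation follows that of TC, hence by less. Apparent benefit in HDL-C, Apo A or vitamin E does not follow.

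The reply does not remove the gap. No sentence makes the between-arm comparison decisive or says which quantity it compares, while the passages that describe benefit both point to change over time.

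**Conclusion.** The point holds as a gap in specification, not as a flaw in the design. The controlled comparison is available and protected, but the plan does not make it the basis for efficacy, and its wording on benefit favours a comparison that regression to the mean can mimic.

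The spurious TC fall of about 3 to 14 mg/dl per arm, and the 21% to 75% chance that at least one inert oil arm shows a significant fall, depend on the assumed mean, SD and reliability and on the qualifying sample being the baseline. With a separate baseline sample this artefact largely disappears. The need to name the deciding contrast does not depend on these figures. This should be fixed before analysis, and it is a free improvement.

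**What to change.** 1. In Statistical analysis, state that the efficacy of each oil yogurt is judged on its Tukey-adjusted contrast with the control yogurt, from an ANCOVA of the follow-up value on arm and the baseline value of the same marker. The arm-by-time term of the repeated-measures model is an acceptable alternative. State that neither the time effect nor the treatment main effect decides efficacy.
2. Reword specific objective 2 and the expected result so that change is compared with the control yogurt.
3. Report within-arm changes descriptively, without p values.
4. State whether the qualifying blood sample is also the baseline.

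The cost is a few sentences in three sections. No new data, samples or participants are needed.
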